6.2.2. Final Analyses

The final analyses of outcomes and planned summaries/listings will be performed on the final locked database through Day 60 and provided in the final report. If data for some of the exploratory endpoints is available, results will also be included in the final report.

6.3. Analysis Populations

The default primary analysis will be based on a modified intention-to-treat (mITT) population, including all subjects who were randomized and received at least one dose of an investigational product administration for all proof of concept stages. If a stage requires a different population for the primary analysis, the appropriate population will be identified in the stage-specific appendix. Safety analyses will be based on the safety population and will use actual treatment received. For some stages an intention-to-treat (ITT) population, which includes all subjects randomized and is analyzed according to the randomized treatment assignment, will be considered. For all populations, actual ordinal score at baseline will be used to classify subjects into baseline ordinal score category.

Stage-specific appendices will denote the appropriate analysis populations to be used if different from the master SAP.

6.3.1. Intention-to-Treat Analysis (ITT) Population

The Intention-to-treat population will include all randomized subjects, and the population will be analyzed using randomized treatment group. Demographics and disposition tables will be based on this population.

6.3.2. Modified Intention-to-Treat (mITT) Population

The mITT population will include all randomized subjects who received at least one dose of an investigational product other than standard of care therapies, and the population will be analyzed using randomized treatment group.

6.3.3. Safety Population

The safety population will include all randomized subjects who received at least one dose of an investigational product other than standard of care therapies, and the population will be analyzed using actual treatment group.

6.4. Covariates and Subgroups

6.4.1. Covariates for the Primary Endpoint

The primary analysis model of ordinal score at Day 8 will use a proportional odds model with baseline steroid use (yes/no) and actual baseline ordinal score (5 vs 6/7) as covariates. A sensitivity analysis of the primary endpoint will include baseline steroid use, actual baseline ordinal score, and categorical variables for sites. Sites will be pooled into categories by grouping sites based on the major US regions (Northeast, Southeast, Midwest, Southwest, and West) groupings include at least 25 subjects who were randomized. A region with less than 25 subjects will be combined with the neighboring region with the fewest subjects. A supplemental analysis of the primary endpoint will include baseline steroid use, actual baseline ordinal score, continuous covariate age, and continuous duration of symptoms prior to enrollment as covariates in the model.

Additional supplemental analyses of the primary endpoint for ordinal score at Day 8 will include baseline steroid use, actual baseline ordinal score, and baseline use (yes/no) of each emerging COVID-19 treatment category listed in Section 6.4.3 as covariates.

A detailed list of covariates and subgroup analyses to be performed for the primary endpoint is also provided in Table 6.

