6.5 Concomitant Therapy

6.5.1 Permitted Concomitant Therapy and Procedures

For patients that are eligible for the study, other therapy received prior to enrollment with any other experimental treatment or off-label use of marketed medications that are intended as specific treatment for COVID-19 or the SARS-CoV-2 infection (i.e., post-exposure prophylaxis [PEP]) are permitted but must be discontinued on enrollment. There is no waiting period between discontinuation of these treatments and administration of study products. However, these prior treatments and their end date should be documented on the concomitant medication form in the EDC system.

Steroids for the treatment of COVID-19 may be used per the local institution's written standard of care (i.e., not just an individual clinician decision) or NIH COVID-19 Treatment Guidelines (https://www.covid19treatmentguidelines.nih.gov/). NIH COVID-19 Treatment Guidelines provide current evidence-based information about the optimal management of COVID-19. NIH COVID-19 Treatment Guidelines were updated on June 25, 2020 to include a Grade AI recommendation for using dexamethasone (6 mg per day for up to 10 days) in patients with COVID-19 who are mechanically ventilated and a Grade B1 recommendation for patients with COVID-19 who require supplemental oxygen but who are not mechanically ventilated based on preliminary data from the RECOVERY trial. The NIH Guidelines also recommend against using dexamethasone in COVID-19 patients who do not require supplemental oxygen.

Steroid regimens for other standard indications including asthma exacerbation, ARDS, COPD, laryngeal edema, adrenal insufficiency, shock, etc. are allowable up to a maximum of prednisone 60 mg daily or equivalent. All steroid use regardless of indication until Day 29 will be recorded in the EDC system.

Subjects who are taking another antiviral for a concurrent infection (e.g. oseltamivir for an influenza virus) or another existing medical condition (e.g. hydroxychloroquine for lupus) may

continue with the treatment. Note that these treatments may be thought of as an off-label medication for COVID-19, however, because they were being used prior to study enrollment for another indication, they are allowable.

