4.5. Efficacy and Safety Variables

For each study day while the subject is hospitalized and follow-up visits, the clinical status will be recorded on an 8- point ordinal scale. The clinical status scale is defined as follows:

1. Not hospitalized, no new or increased limitations on activities;
2. Not hospitalized, but new or increased limitation on activities and/or requiring new or increased home oxygen, CPAP or BiPAP;
3. Hospitalized, not requiring new or increased supplemental oxygen* - no longer requires ongoing medical care;
4. Hospitalized, not requiring new or increased supplemental oxygen* - requiring ongoing medical care (COVID-19 related or otherwise);
5. Hospitalized, requiring new or increased supplemental oxygen*;
6. Hospitalized, requiring new or increased non-invasive ventilation or high flow oxygen devices;
7. Hospitalized, on invasive mechanical ventilation or ECMO;
8. Death.

The National Early Warning Score (NEWS) has demonstrated an ability to discriminate subjects at risk of poor outcomes [1]. This score is based on 7 clinical parameters (see Table 3). The NEWS is collected at baseline as a measure of ordinal score. It can be performed concurrently with the Ordinal Scale.

The 7 parameters can be obtained from the hospital chart or electronic medical record (EMR) using the last measurement prior to the time of assessment and a numeric score given for each parameter (e.g., a RR of 9 is one point, oxygen saturation of 92 is two points). The NEWS is recorded for the day on which it is obtained. ECMO and mechanical ventilated subjects should be assigned a score of 3 for respiratory rate (RR<8) regardless of the ventilator setting. Subjects on ECMO should get a score of 3 for heart rate since they are on cardiopulmonary bypass.

Table 3: National Early Warning Score (NEWS)

PHYSIOLOGICAL PARAMETERS	3	2	1	0	1	2	3
Respiration Rate	≤8		9 - 11	12 - 20		21 - 24	≥25
Oxygen Saturations	≤91	92 - 93	94 - 95	≥96			
Any Supplemental Oxygen		Yes		No			
Temperature	≤35.0		35.1 - 36.0	36.1 - 38.0	38.1 - 39.0	≥39.1	
Systolic BP	≤90	91 - 100	101 - 110	111 - 219			≥220
Heart Rate	≤40		41 - 50	51 - 90	91 - 110	111 - 130	≥131
Level of Consciousness				A			V, P, or U

Level of consciousness = alert (A), and non-alert and arousable only to voice (V) or pain (P), and unresponsive (U).

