6.4.2. Covariates for Secondary Endpoints

The main analysis for time to sustained recovery will use baseline steroid use and actual baseline ordinal score as covariates in a Cox regression model. P-value from the score test of this adjusted Cox model will be used to compare the covariate adjusted time to sustained recovery between treatment arms. This analysis will be referred to as the primary analysis of the time to sustained recovery endpoint. In the supplemental analysis, time to sustained recovery endpoint will be analyzed using baseline steroid use, actual baseline ordinal score, continuous age, and continuous duration of symptoms prior to enrollment as covariates in the Cox model.

Survival without respiratory failure up to and including Study Day 29 will be analyzed only for subjects with an actual baseline ordinal score of 5 or 6. The main analysis for this endpoint will use a logistic regression model adjusted for baseline ordinal score (5 vs 6/7), baseline dexamethasone use (yes or no), continuous

baseline CRP value, and continuous age as covariates. Additionally, the proportion of subjects who are alive and without respiratory failure up to and including Study Day 29 will be presented by treatment along with 95% and 80% CI estimated from Kaplan Meier. As a sensitivity analysis, survival without respiratory failure will be analyzed using a logistic regression model adjusting for baseline steroid use and actual baseline ordinal score as covariates. A supplemental analysis of this endpoint will use a logistic regression model adjusting for baseline steroid use, actual baseline ordinal, continuous age, and continuous duration of symptoms prior to enrollment.

The analysis of the time to mechanical ventilation or death will include baseline ordinal score (5 vs 6/7), baseline dexamethasone use (yes or no), baseline CRP value and age as covariates in the Cox regression model.

A detailed list of covariates and subgroup analyses to be performed for secondary endpoints is also provided in [Table 6](#).

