For analyses based on multiple imputation, remaining missing ordinal scores will be imputed for Day 8 using the PROC MI procedure in SAS. Treatment group (trtvar), baseline ordinal score (basesteroidusevar), baseline steroid use (basesteroidvar), duration of symptoms prior to randomization (dursymp), age, indicator for black or Hispanic ethnicity (blackhispl), presence of 2 or more comorbidities (comorb2fl), baseline CRP (basecrp), and indicator for discharge to a location other than long term care facility (LTAC), hospice care or another hospital (i.e., good discharge status) at the last assessment of the subject being imputed will be included as covariates in the multiple imputation model for ordinal scores at each timepoint using monotone logistic regression. The good discharge status variable at last assessment variable (goodischstat) will vary from subject to subject and will be defined as the discharge status for all subjects at the last assessed timepoint of the subject being imputed. For example, if the subject being imputed had their last assessment at Day 5, the good discharge status variable for all subjects will be defined as their discharge status at Day 5. The timing for the discharge status variable will be defined according to the last assessment timepoint of the subjects being imputed. The treatment group variable (trtvar) represents the randomized treatment group. Each imputation model will include all subjects with complete data plus all subject with missing ordinal score at Day 8 to be imputed who have the same last assessment day. The procedure will loop through all possible last assessment days (i.e., day 1 through day 8) imputing data for subjects missing data who were last assessed on the same day.

Since missing data in any of these baseline characteristics may cause issues with the monotone missing data patterns, the following methods will be used to fill in missing baseline covariates data:

- For continuous baseline covariates (age, CRP, duration of symptoms), mean imputation will be used to replace missing values with the overall mean value from all randomized subjects for the given covariate.
- For indicator variables of baseline steroid use, black or Hispanic ethnicity, and presence of two or more comorbidities, subjects with missing values will be given the value with the greatest number of subjects among all randomized subjects.
- We do not anticipate any missing data for actual baseline ordinal score.

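### The main Day 8 and time-to-sustained-recovery models leave continuous age to supplemental runs, although other main models in the SAP include it; if age is prognostic, some power is lost at no saving

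*SAP*

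**What the plan says.** SAP 6.4.1 states that the main Day 8 analysis "will use a proportional odds model with baseline steroid use (yes/no) and actual baseline ordinal score (5 vs 6/7) as covariates". SAP 6.4.2 gives the first key secondary endpoint the same pair: "The main analysis for time to sustained recovery will use baseline steroid use and actual baseline ordinal score as covariates in a Cox regression model". Table 6 repeats both.

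Age enters these two endpoints only at a lower tier. For Day 8, "A supplemental analysis of the primary endpoint will include baseline steroid use, actual baseline ordinal score, continuous covariate age", with symptom duration added as well. The supplemental recovery model is built the same way.

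Elsewhere the SAP gives age a main role:
- The main logistic model for survival without respiratory failure, the other key secondary endpoint, lists "baseline CRP value, and continuous age as covariates" (6.4.2, Table 6).
- The Cox model for time to ventilation or death also includes age and CRP (6.4.2, Table 6).
- The imputation model for the Day 8 score includes "duration of symptoms prior to randomization (dursymp), age, indicator for black or Hispanic ethnicity" and further baseline variables (6.5.2).

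Baseline NEWS is collected, summarised and listed, but enters no efficacy model. These are the master SAP's defaults, which its Preface says follow BET-A closely and which a stage-specific appendix may override.

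**The concern.** Leaving a prognostic baseline variable out of a proportional-odds or Cox model pulls the treatment ratio toward 1 and lowers the power of its test, even when the arms are balanced on that variable. SAP 5 calls an agent promising at a final p below 0.20 and significant below 0.05, with 100 per arm. A supplemental analysis does not settle either label. Age is collected for everyone and is already trusted as a covariate in neighbouring models, so any precision it offers would be unused in the one analysis that decides, and in the lead analysis of recovery.

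**Working it through.** **1. Reproduce the plan's figure.** Inputs: Table 4 control distribution, 100 per arm at 1:1, two-sided tests (SAP 5). Control cumulative proportions from category 2 to category 7 are 0.346, 0.358, 0.464, 0.635, 0.723 and 0.965. At an odds ratio of 2 each becomes 2c/(1+c): 0.514, 0.527, 0.634, 0.777, 0.839 and 0.982. Averaging the two arms' category probabilities gives a sum of cubes of about 0.092. Solving the SAP 5 formula for total N = 200:

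z(α/2) + z(β) = √[200 × (ln 2)² × (1 − 0.092) / 12] = √[200 × 0.4805 × 0.908 / 12] = 2.70

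Power at 0.05 is Φ(2.70 − 1.96) = 0.769; at 0.20 it is Φ(2.70 − 1.28) = 0.921. A simulation of 20,000 trials with the interim futility look gave 0.764 and 0.911, against Table 5's 0.765 and 0.913. Table 5 therefore reproduces with no covariates in the model.

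**2. Day 8 with and without age.** The documents give no prognostic strengths, so these are assumed: half the patients at score 6/7; log odds ratio 2.0 for 6/7 against 5; 90% steroid use, unrelated to outcome; log odds ratio per SD of 0.2 to 0.8 for age and 0 to 0.6 for NEWS beyond ordinal score. The treatment effect was set so that the odds ratio adjusted for ordinal score is 2.0. There were 3,000 trials of 200 patients per row, with no interim look. Power at alpha 0.05 / 0.20:

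| Age, NEWS (log OR per SD) | SAP covariates | SAP covariates + age | Ordinal score + age + NEWS |
|---|---|---|---|
| 0.2, 0 | 0.711 / 0.884 | 0.714 / 0.885 | 0.711 / 0.887 |
| 0.4, 0.2 | 0.715 / 0.894 | 0.740 / 0.904 | 0.743 / 0.909 |
| 0.6, 0.4 | 0.739 / 0.911 | 0.780 / 0.929 | 0.801 / 0.934 |
| 0.8, 0.6 | 0.746 / 0.910 | 0.814 / 0.942 | 0.843 / 0.958 |

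- Age alone at 0.05 gains 0.3, 2.5, 4.1 and 6.8 points. The last row assumes an odds ratio of exp(0.8) = 2.2 per SD; the third assumes 1.8.
- Age plus NEWS gains 0.0, 2.8, 6.2 and 9.7 points at 0.05, and 0.3, 1.5, 2.3 and 4.8 at 0.20.
- The average estimated odds ratio moves from 1.98, 1.99, 2.02 and 2.03 to 1.99, 2.04, 2.12 and 2.20 when age is added, which is the pull toward 1 being undone.
- At an odds ratio of 1.5 and alpha 0.20, age alone takes power from 0.584 to 0.601 and from 0.606 to 0.641 in the two middle cases.

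The Monte Carlo standard error of one power figure is √(0.73 × 0.27 / 3000) = 0.008, so the first row shows no gain. Levels here should not be set against Table 5, because the odds ratio of 2 is defined after adjustment for ordinal score.

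**3. A second set of assumptions.** With 60% at score 5, log odds ratio 1.5 for 6/7, 85% steroid use, age odds ratio 1.4 to 1.7 per SD and 900 trials per case, power at 0.05 went from 0.74 to 0.74 (weak age effect) and from 0.70 to 0.75 (strong). That equals about 4% to 12% more subjects: 0.04 × 200 = 8 to 0.12 × 200 = 24. With no age effect the two models had power 0.732 and 0.734.

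**4. Recovery.** Cox model, assumed hazard ratio 1.5, 200 patients, 2,500 trials, 92% to 95% recovering by Day 60. Moving from the SAP covariates to ordinal score, age and NEWS, power at 0.05 went from 0.771 to 0.790 (log hazard ratio per SD 0.15 for age, none for NEWS), 0.776 to 0.836 (0.3, 0.15) and 0.776 to 0.914 (0.5, 0.3). Only the first case isolates age.

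**5. The steroid term.** Adding it to a model with ordinal score raised the treatment standard error by about 0.4%. Power was 0.734 without it, and 0.731, 0.738, 0.734 and 0.732 with it at 50%, 90%, 95% and 98% use.

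**The case against.** The two covariates were chosen, not overlooked. SAP 15.2 records that they replaced the stratification variables, and that the respiratory-failure model was adjusted to match BET-B, which is alignment across stages rather than a view on Day 8. An imputation model richer than the analysis model is ordinary practice. Age-adjusted results are already pre-specified for both endpoints, ordinal score already carries much of the severity information, and this is a proof-of-concept screen whose Table 5 power does not rely on covariates. All of that stands, and it keeps the point modest. None of it is a reason to leave age out of the deciding models.

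Three stronger readings are tempting, and the documents do not support them.

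- **That the steroid flag wastes power.** The protocol cites a "Grade B1 recommendation for patients with COVID-19 who require supplemental oxygen but who are not mechanically ventilated", and also one for ventilated patients, so a reader may infer near-universal use. No baseline rate is stated, and even at 98% use the term costs next to nothing. At worst it adds little.
- **That NEWS must be added.** SAP 4.5 says "The National Early Warning Score (NEWS) has demonstrated an ability to discriminate subjects at risk of poor outcomes", but the same section presents baseline NEWS as a gauge of the ordinal score. Everyone enrolled needs oxygen or ventilation, so the oxygen item hardly varies. Ventilated and ECMO patients receive a fixed respiratory-rate score, and ECMO patients a fixed heart-rate score. Its value beyond ordinal score is assumed in the simulations, not shown.
- **That Table 5 is wrong.** It reproduces without covariates.

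**Conclusion.** The point holds for age. Both main models omit it, although the SAP relies on it in two other main models and in the imputation of the same Day 8 score, and no reason for the difference is given. At an odds ratio of 2 and alpha 0.05, the cost on Day 8 is about 0 to 5 points of power for age alone, for assumed age odds ratios up to about 1.8 per SD; only the extreme case of 2.2 per SD reached about 7. Adding NEWS as well widens the range to about 0 to 10 points at 0.05 and 0 to 5 at 0.20. For recovery, age plus NEWS gave about 2 to 14 points under an assumed hazard ratio of 1.5. These ranges rest on assumed prognostic strengths and include no gain on Day 8; no simulated case showed a material loss. This is a worthwhile improvement, not a flaw that invalidates the plan.

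**What to change.** Before unblinding, change SAP 6.4.1, 6.4.2, Table 6 and the model code so that the main Day 8 proportional-odds model and the main sustained-recovery Cox model adjust for baseline ordinal score, baseline steroid use and continuous age. Bring the covariate wording in 8.1 into line. Keep the present two-covariate models as sensitivity analyses. The supplemental models will then differ from the main ones only by symptom duration.

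The imputation model already contains age, and 6.5.2 already has a mean-fill rule for missing age, so neither needs changing. Keep the steroid term. Baseline NEWS is optional; if it goes into the Day 8 model, add it to the imputation model in 6.5.2 too, so that the imputation model contains every covariate in the analysis.

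The cost is wording and one extra term per model, with no new data. The only downside is that the odds ratio or hazard ratio becomes conditional on age and should be reported as such.

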6.4.2. Covariates for Secondary Endpoints

The main analysis for time to sustained recovery will use baseline steroid use and actual baseline ordinal score as covariates in a Cox regression model. P-value from the score test of this adjusted Cox model will be used to compare the covariate adjusted time to sustained recovery between treatment arms. This analysis will be referred to as the primary analysis of the time to sustained recovery endpoint. In the supplemental analysis, time to sustained recovery endpoint will be analyzed using baseline steroid use, actual baseline ordinal score, continuous age, and continuous duration of symptoms prior to enrollment as covariates in the Cox model.

Survival without respiratory failure up to and including Study Day 29 will be analyzed only for subjects with an actual baseline ordinal score of 5 or 6. The main analysis for this endpoint will use a logistic regression model adjusted for baseline ordinal score (5 vs 6/7), baseline dexamethasone use (yes or no), continuous

baseline CRP value, and continuous age as covariates. Additionally, the proportion of subjects who are alive and without respiratory failure up to and including Study Day 29 will be presented by treatment along with 95% and 80% CI estimated from Kaplan Meier. As a sensitivity analysis, survival without respiratory failure will be analyzed using a logistic regression model adjusting for baseline steroid use and actual baseline ordinal score as covariates. A supplemental analysis of this endpoint will use a logistic regression model adjusting for baseline steroid use, actual baseline ordinal, continuous age, and continuous duration of symptoms prior to enrollment.

The analysis of the time to mechanical ventilation or death will include baseline ordinal score (5 vs 6/7), baseline dexamethasone use (yes or no), baseline CRP value and age as covariates in the Cox regression model.

A detailed list of covariates and subgroup analyses to be performed for secondary endpoints is also provided in [Table 6](#).

6.4.3. Subgroups

The following subgroups will be considered for the different subgroup analyses:

- Severity of disease using actual baseline ordinal score
 - Actual baseline ordinal score 5: Hospitalized and requiring supplemental oxygen
 - Actual baseline ordinal score 6 or 7: Hospitalized, on non-invasive ventilation or high-flow oxygen devices; or Hospitalized, on invasive mechanical ventilation or ECMO
- Baseline steroid use (Yes; No)
- Baseline use of emerging COVID-19 treatments (Yes; No): Defined by the sponsor based on a blinded review of WHODrug coded medications.
- Duration of symptoms prior to enrollment
 - Quartiles
 - \leq Median; $>$ Median
- Race (White; Black/African American; Asian; Other)
- Ethnicity (Hispanic or Latino; Not Hispanic or Latino)
- Comorbidities
 - None; Any
 - One, Two or more
 - Obese; Non-Obese
- Age (<40 ; 40-64; 65 and older),
- Sex (Female; Male)

Refer to [Table 6](#) for details of which specific subgroup variables will be considered for a given endpoint.

Interaction tests will be conducted to evaluate whether the effect of treatment is different among subgroups described above for primary and key secondary endpoints. The type III p-value for the interaction term from the primary analysis of the primary endpoint, the primary analysis of the time to sustained recovery endpoint,

and the primary analysis of the survival without respiratory failure endpoint with the addition of the interaction term(s) will be reported.

A review of the concomitant medications will be performed by the study sponsor using the 202003 version of WHODrug to identify emerging COVID-19 treatments focusing on medications that fall into the following categories:

- Other drugs used to treat COVID (off-label, experimental use)
 - Monoclonal antibodies targeting the spike protein of SARS-CoV-2 including casirivimab, imdevimab and bamlanivimab
- Corticosteroids
- Other anti-inflammatory drugs:
 - JAK inhibitors: Tofacitinib, Baricitinib, etc
 - Tyrosine kinase inhibitors: Ruxolitinib, etc
 - Interleukin inhibitors

Additional details regarding covariates used in primary, sensitivity and supplemental analyses along with subgroup analyses to be performed for each endpoint are provided below in [Table 6](#).

Table 6: Covariates and Subgroup Analyses for Each Endpoint

Endpoint	Analysis	Covariates/Subgroups
Primary Endpoint		
1. Ordinal Score at Day 8	Primary	1. Adjust for the following covariates: 
 • Baseline steroid use • Actual baseline ordinal score
	Sensitivity	1. Repeat primary analysis with the following covariates: 
 • Baseline steroid use • Actual baseline ordinal score • Site pooled by geographic regions (Categorical) 2. Repeat primary analysis on ITT population with the following covariates: 
 • Baseline steroid use • Actual baseline ordinal score
	Supplemental	1. Adjust for the following covariates: 
 • Baseline steroid use • Actual baseline ordinal score • Continuous Age • Continuous duration of symptoms prior to enrollment 2. Repeat primary model with the following covariates: 
 • Baseline steroid use • Actual baseline ordinal score • Baseline use of emerging COVID-19 treatment by treatment categories
	Subgroup	Repeat the primary analysis for this endpoint within each of the following subgroups: 
 • Actual baseline ordinal score • Baseline steroid use • Baseline use of emerging COVID-19 treatments • Duration of symptoms prior to enrollment • Race • Ethnicity • Comorbidities • Age (categorical) • Sex Baseline steroid use and baseline ordinal score will be included in the subgroup analysis as covariates unless the covariate is the subgroup.
Key Secondary Endpoints		
1. Time to Sustained Recovery	Primary	1. Adjust for the following covariates: 
 • Baseline steroid use • Actual baseline ordinal score
	Supplementary	1. Adjust for the following covariates: 
 • Baseline steroid use • Actual baseline ordinal score • Age (continuous) • Duration of symptoms prior to enrollment (continuous)

Endpoint	Analysis	Covariates/Subgroups
	Subgroup	Repeat the primary analysis for this endpoint within each of the following subgroups: 
 • Actual baseline ordinal score • Baseline steroid use • Baseline use of emerging COVID-19 treatments • Duration of symptoms prior to enrollment • Race • Ethnicity • Comorbidities • Age (categorical) • Sex Baseline steroid use and baseline ordinal score should be included in the subgroup analysis as covariates unless the covariate is the subgroup.
2. Survival without respiratory failure up to and including Study Day 29	Primary	1. Adjust for the following covariates: 
 • Baseline dexamethasone use • Actual baseline ordinal score • Baseline CRP value (continuous) • Age (continuous)
	Sensitivity	1. Adjust for the following covariates: 
 • Baseline steroid use • Actual baseline ordinal score
	Supplementary	1. Adjust for the following covariates: 
 • Actual baseline ordinal score • Baseline dexamethasone use • Age (continuous) • Duration of symptoms prior to enrollment (continuous)
	Subgroup	Repeat the primary analysis for this endpoint within each of the following subgroups: 
 • Actual baseline ordinal score • Baseline steroid use • Baseline dexamethasone use • Baseline use of emerging COVID-19 treatments • Duration of symptoms prior to enrollment • Race • Ethnicity • Comorbidities • Age (categorical) • Sex • Baseline CRP <150 Baseline dexamethasone use, baseline CRP, age, and baseline ordinal score will be included in the subgroup analysis as covariates unless the covariate is the subgroup.

Endpoint	Analysis	Covariates/Subgroups
Other Secondary Endpoints: Efficacy		
1. Time to 1-point improvement by Day 60	Primary	Adjust for the following covariates: 
 • Baseline steroid use • Actual baseline ordinal score
	Subgroup	Repeat the primary analysis for this endpoint within each of the following subgroups: 
 • Actual baseline ordinal score • Baseline steroid use • Baseline use of emerging COVID-19 treatments • Duration of symptoms prior to enrollment Baseline steroid use and baseline ordinal score will be included in the subgroup analysis as covariates unless the covariate is the subgroup.
2. Time to 2- points improvement by Day 60	Primary	Adjust for the following covariates: 
 • Baseline steroid use • Actual baseline ordinal score
	Subgroup	Repeat the primary analysis for this endpoint within each of the following subgroups: 
 • Actual baseline ordinal score • Baseline steroid use • Baseline use of emerging COVID-19 treatments • Duration of symptoms prior to enrollment Baseline steroid use and baseline ordinal score will be included in the subgroup analysis as covariates unless the covariate is the subgroup.
3. Clinical status assessed using ordinal scale on Study Days 1, 3, 5, 8, 11, 15, 22, and 29; Change in clinical status using change in ordinal scale from Study Day 1 to Study Days 3, 5, 8,11, 15, 22 and 29.	Primary	
 • No covariate adjustment
	Subgroup	Repeat the primary analysis for this endpoint within each of the following subgroups: 
 • Actual baseline ordinal score
4. Days of supplemental oxygen by Study Day 29;	Primary	
 • No covariate adjustment
	Subgroup	Repeat the primary analysis for this endpoint within each of the following subgroups: 
 • Actual baseline ordinal score • Baseline steroid use • Baseline use of emerging COVID-19 treatment • Duration of symptoms prior to enrollment (only using the <= Median; > Median classification)
5. Days of non-invasive ventilation/high-flow oxygen by Study Day 29;	Primary	
 • No covariate adjustment for this analysis
	Subgroup	Repeat the primary analysis for this endpoint within each of the following subgroups: 
 • Actual baseline ordinal score • Baseline steroid use • Baseline use of emerging COVID-19 treatment

Endpoint	Analysis	Covariates/Subgroups
		
 Duration of symptoms prior to enrollment (only using the \leq Median; $>$ Median classification)
6. Incidence of new non-invasive oxygen use (clinical status > 5) during the study up to and including Study Day 29 for subject with baseline clinical status of 5;	Primary	
 No covariate adjustment for this analysis
7. Days a subject who has a baseline clinical status of 5 has a clinical status > 5 up to and including Study Day 29;	Primary	
 No covariate adjustment for this analysis
	Subgroup	Repeat the primary analysis for this endpoint within each of the following subgroups: 
 Actual baseline ordinal score Baseline steroid use Baseline use of emerging COVID-19 treatment Duration of symptoms prior to enrollment (only using the \leq Median; $>$ Median classification)
8. Days of invasive mechanical ventilation/ECMO by Study Day 29;	Primary	
 No covariate adjustment for this analysis
	Subgroup	Repeat the primary analysis for this endpoint within each of the following subgroups: 
 Actual baseline ordinal score Baseline steroid use Baseline use of emerging COVID-19 treatments Duration of symptoms prior to enrollment (only using the \leq Median; $>$ Median classification)
9. Incidence of new invasive ECMO use through study Day 29 for subjects with baseline clinical status of 5 or 6;	Primary	
 No covariate adjustment
10. Days a subject who has a baseline clinical status of 5 or 6 has a clinical status > 6 up to and including Study Day 29;	Primary	
 No covariate adjustment
	Subgroup	Repeat the primary analysis for this endpoint within each of the following subgroups: 
 Actual baseline ordinal score Baseline steroid use Baseline use of emerging COVID-19 treatment Duration of symptoms prior to enrollment (only using the \leq Median; $>$ Median classification)
11. Proportion of subjects alive and without respiratory failure at Study Day 29;	Primary	
 No covariate adjustment
12. Time (days) to death or ventilation up to and Including Day 29	Primary	Adjust for the following covariates: 
 Baseline dexamethasone use Actual baseline ordinal score Baseline CRP value (Continuous) Age (continuous)

Endpoint	Analysis	Covariates/Subgroups
13. Days of hospitalization from date of admission by Study Day 29.	Primary	
 No covariate adjustment for this analysis
	Subgroup	Repeat the primary analysis for this endpoint within each of the following subgroups: 
 Actual baseline ordinal score Baseline steroid use Baseline use of emerging COVID-19 treatment Duration of symptoms prior to enrollment (only using the <= Median; > Median classification)
Other Secondary Endpoints: Safety		
1. Values of CRP ferritin, D-dimer, LDH, and fibrinogen on Study Day 1: Study Days 3, 5, 8, 11,15 and 29	Primary	
 No covariate adjustment
2. 14-day Mortality	Primary	1. Adjust for the following covariates: 
 Actual baseline ordinal score Baseline steroid use
3. 28-day Mortality	Primary	1. Adjust for the following covariates: 
 Actual baseline ordinal score Baseline steroid use
4. 59-day Mortality	Primary	1. Adjust for the following covariates: 
 Actual baseline ordinal score Baseline steroid use
	Sensitivity	1. Adjust for the following covariates: 
 Actual baseline ordinal score Baseline steroid use
5. Time to death by Day 29	Primary	
 No covariate adjustment
	Sensitivity	
 No covariate adjustment
6. SAEs by Day 60	Primary	
 No covariate adjustment
7. Grade 3 or 4 AE by Day 60	Primary	
 No covariate adjustment
8. Time to Death, SAE or Grade 3 or 4 TEAE	Primary	
 No covariate adjustment
9. Episodes of early discontinuation or interruption of study product administration;	Primary	
 No covariate adjustment
10. Values of WBC with differential, hemoglobin, platelets, creatinine, total bilirubin, ALT, AST, and INR on Study Day 1; Study Days 3, 5, 8, and 11 (while hospitalized); and Study Days 15 and 29 (if	Primary	
 No covariate adjustment

Endpoint	Analysis	Covariates/Subgroups
attends in-person visit or still hospitalized).		
Exploratory Endpoints		
1. Concomitant COVID-19 treatments (e.g., steroids) post-baseline up to and including Study Day 29.	Primary	
 No covariate adjustment

